## 6.17. Planned Exploratory Analyses

The planned exploratory analyses are described in Section 4.3 and [Appendix 3](#).

## 6.18. Annual Report Analyses

Annual report analyses, such as the Development Update Safety Report, will be documented in a separate analysis plan.

## 6.19. Clinical Trial Registry Analyses

Additional analyses will be performed for the purpose of fulfilling the Clinical Trial Registry (CTR) requirements.

Analyses provided for the CTR requirements include a summary of AEs, provided as a dataset which will be converted to an XML file. Both SAEs and ‘Other’ AEs are summarized by treatment group and by MedDRA PT.

- An AE is considered ‘Serious’ whether or not it is a TEAE.
- An AE is considered in the ‘Other’ category if it is both a TEAE and is not serious. For each SAE and ‘Other’ AE, for each term and treatment group, the following are provided:
  - the number of participants at risk of an event
  - the number of participants who experienced each event term
  - the number of events experienced
- Consistent with [www.ClinicalTrials.gov](http://www.ClinicalTrials.gov) requirements, ‘Other’ AEs that occur in fewer than 5% of patients/subjects in every treatment group may not be included if a 5% threshold is chosen (5% is the minimum threshold).
- Adverse event reporting is consistent with other document disclosures (e.g., clinical study report, manuscripts).

Similar methods will be used to satisfy the European Clinical Trials Database requirements.

## 7. Unblinding Plan

Refer to the blinding and unblinding plan document for details.

## Appendix 1. Dose Conversion for Corticosteroid

In case conversion of dosage of corticosteroids is needed, the following table should be used for converting nonprednisone medications to prednisone equivalent:

Multiply the dose of the corticosteroid taken by the patient (in milligrams) in Column 1 by the conversion factor in Column 2 to get the equivalent dose of prednisone (in milligrams).

*Example: Patient is taking 16 mg of methylprednisolone po daily. To convert to prednisone: 16 mg methylprednisolone  $\times$  1.25 = 20 mg prednisone. 16 mg of methylprednisolone po daily is equivalent to 20 mg of prednisone po daily.*

Column 1	Column 2
Corticosteroid Preferred Term	Conversion factor for converting to an equivalent prednisone dose
Prednisone	1
Prednisone acetate	1
Prednisolone	1
Prednisolone acetate	1
Prednisolone sodium phosphate	1
Methylprednisolone	1.25
Methylprednisolone acetate	1.25
Methylprednisolone sodium succinate	1.25
Triamcinolone	1.25
Triamcinolone acetonide	1.25
Triamcinolone hexacetonide	1.25
Cortisone	0.2
Cortisone acetate	0.2
Hydrocortisone	0.25
Hydrocortisone acetate	0.25
Hydrocortisone sodium succinate	0.25
Betamethasone	6.25
Betamethasone acetate	6.25
Betamethasone dipropionate	6.25
Betamethasone sodium phosphate	6.25
Dexamethasone	6.25
Dexamethasone acetate	6.25
Dexamethasone phosphate	6.25
Dexamethasone sodium phosphate	6.25

Column 1	Column 2
Corticosteroid Preferred Term	Conversion factor for converting to an equivalent prednisone dose
Paramethasone	2.5
Deflazacort	0.83
Celestona bifas	6.25
Depo-Medrol med lidocaine	1.25
Diprosan	6.25
Fluocortolone	1
Meprednisone	1.25

---

## Appendix 2. Multiple Imputation

---

### 1) Unique challenges for multiple imputation of the NIAID-OS:

While many methods of multiple imputation (and single imputation) are readily available in standard software, the NIAID-OS in KHAA presents several unique problems. First, it includes an absorbing state of death (NIAID-OS = 8). Also, complete recovery (NIAID-OS = 1) is ordinarily an absorbing state with some exceptions where patients become sick again. Second, change between days is generally slow. Patients often stay in the same state for several days. Thus, the correlation between days is very strong which may cause issues of (near) multicollinearity when fitting regression models for use in imputation. Also, some methods may not converge when many highly correlated days are being imputed for a patient. Third, standard assumptions such as multivariate normality and approximate linearity are highly suspect for the NIAID-OS. Finally, for study KHAA additional information is available for some patients. For example, for many patients the exact NIAID-OS score is missing for some days, but it may be inferred from other available data that the patient is not dead (i.e., NIAID OS  $\neq$  8). It would be beneficial to use an imputation technique which can make use of this information.

For these reasons, a novel Markov model multiple imputation (MMMI) method is adopted to impute the NIAID-OS scores. A simulation study was performed to show the operating characteristics of the suggested method. The manuscript for this method is currently under preparation and the results of the simulation study are available upon request.

### 2) Overview of multiple imputation using a Markov model:

A Markov model assumes that each transition to a future state is dependent on only the previous state. Let  $H_{it} \in \{1, 2, \dots, 8\}$  be a random variable representing the sequence of NIAID-OS states for individual  $i \in \{1, 2, \dots, N\}$  on day  $t \in \{1, 2, \dots, T\}$ . The parameters of interest in a Markov model are the initial probabilities and the transition probabilities:

Initial Probabilities: Let  $\pi_j$  represent the probability that a patient will be in state  $j$  on Day 1.

Transition Probabilities: Let  $P_{b_t}(k|j)$  be the probability of transitioning from ordinal state  $k \in \{1, 2, \dots, 8\}$  to state  $j \in \{1, 2, \dots, 8\}$  on day  $t$  to day  $t + 1$ . Here  $b_t$  represents a bin associated with a transition from day  $t$  to day  $t + 1$ . We assume that within each bin the transition probabilities are the same. Daily transitions were divided into 4 bins as follows: (bin 1) includes the first 6 transitions; (bin 2) includes the next 7 transitions; (bin 3) includes the next 7 transitions; and (bin 4) the final 7 transitions.

The parameters  $\boldsymbol{\pi}$  and  $\boldsymbol{P}$  are collectively referred to as  $\boldsymbol{\theta}$ . We let  $\mathbf{h}_{1:T}$  represent a vector of states of length  $T$ , and  $\mathbf{h}_{i,1:T}^{obs}$  represent the observed scored for individual  $i$ . Also we define the set  $S_{iT} = \{\text{All possible trajectories } \mathbf{h} \text{ s.t. consistent with observed data } \mathbf{h}_i^{obs}\}$ . The set may be constructed to account for complex types of missingness such as knowing that a patient is not dead.

The likelihood for the Markov model for a single individual  $i$  may be written by marginalizing out the missing scores:

$$\begin{aligned} l_i(\boldsymbol{\pi}, \mathbf{P} | \mathbf{h}_{i,1:T}^{obs}) &= \sum_{\mathbf{h} \in \mathcal{S}_{iT}} P(H_{i1} = h_1, \dots, H_{iT} = h_t) \\ &= \sum_{\mathbf{h} \in \mathcal{S}_{iT}} \pi_{h_1} \prod_{t=2}^T P_{b_{t-1}}(h_t | h_{t-1}) \end{aligned}$$

The overall likelihood may be found by multiplying together the likelihoods from each patient. As described by Rubin (1976) the maximum likelihood estimator after marginalizing out the missing observations is still asymptotically unbiased under a missing at random (MAR) assumption. Maximum likelihood estimates of the model parameters ( $\boldsymbol{\theta}$ ) may be calculated using the expectation maximization (EM) algorithm. The same algorithms commonly used for “hidden Markov models” (HMMs) may be equally applied to the Markov model with missing data. The EM algorithm in this context is known as the Baum-Welsh algorithm in the HMM literature. A standard algorithm can be used to simulate from the distribution of the missing data conditional on the observed data (i.e., simulate from  $\mathbf{P}_{\boldsymbol{\theta}}(\mathbf{H}_i^{mis} | \mathbf{H}_{i,1:T}^{obs})$ ).

As described by Honaker and King (2010), a bootstrap + EM procedure is used to appropriately account for model uncertainty. The imputation proceeds by performing the following steps for  $m \in \{1, 2, \dots, M\}$  with  $M = 100$ :

1. Generate a bootstrapped dataset by resampling patients with replacement.
2. Estimate the model parameters using the maximum likelihood approach as calculated using the EM algorithm. For iteration  $m$  the bootstrapped parameter estimates are  $\tilde{\boldsymbol{\theta}}_m$ .
3. Impute the missing data in the original data (i.e., not the bootstrap data) by simulating from the distribution of the missing states conditional on the observed states assuming the estimated bootstrap model parameters (i.e., simulate from  $\mathbf{P}_{\tilde{\boldsymbol{\theta}}_m}(\mathbf{H}_i^{mis} | \mathbf{H}_{i,1:T}^{obs})$ ).

The above steps are applied 100 times to generate 100 multiply imputed datasets. We note that with MMMI covariates can be accounted for by using a stratified imputation approach where imputation is performed separately for each strata. The mathematical details of the MMMI algorithm is provided in the following section.

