## 8.1. Efficacy Assessments

## 8.1.1. COVID-19 Clinical Status Assessment

The COVID-19 Clinical Status Assessment will be used to collect components needed to derive scores for the ordinal scales used in this study. This assessment will also collect the use of proning and reason for discontinuation of invasive mechanical ventilation.

The assessment will be completed on each day of the study by entering the assessment for the previous day (that is, midnight to midnight; 00:00 - 23:59 [24 hour clock]).

On Day 1, the patient's status at randomization will be reported.

On Day 2 the status will be reported for the period from randomization to midnight on Day 1.

The patient's clinical status will be captured daily through Day 29.

The hospitalization portion of the patient's clinical status will be completed daily, regardless of patient's discharge status or patient contact.

The patient's clinical status reflecting data for Day 28 (midnight to midnight) will be recorded in the Day 29 eCRF.

A clinical status assessment will be conducted via telephone visit for Day 60.

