### 6.4.3. Multiple Imputation

A multiple imputation method will be used to impute the missing NIAID-OS scores (Rubin, 1996). The multiply-imputed datasets will be used for the primary analyses of several endpoints involving the NIAID-OS scores. A total of 100 multiply-imputed datasets will be generated. For random number generation, the seed will be set 3012021. The multiple imputation will be performed in a stratified manner with the imputation performed separately for each of the following levels: (1) baricitinib patients with baseline NIAID-OS of 5 or 6 and baseline steroid use, (2) baricitinib patients with baseline NIAID-OS of 5 or 6 and no baseline steroid use, (3) other baricitinib patients, (4) comparator patients with baseline NIAID-OS of 5 or 6 and baseline steroid use, (5) comparator patients with baseline NIAID-OS of 5 or 6 and no baseline steroid use, and (6) other comparator patients. In all these strata, baseline steroid use is defined as in Section 6.1.4. These strata are slightly reduced from what might be expected in order to keep a sufficient number of patients in each stratum. Imputation will be performed using a Markov model where each transition to a future state is dependent on only the previous state. This approach is described in detail in [Appendix 2](#).

The intended estimand for the multiple imputation approach is based on the treatment policy strategy for handling intercurrent events (ICH E9R [ICH 2017]). In this strategy the value of the NIAID-OS score is the value of interest regardless of any intercurrent events that occurred. The NIAID-OS includes a state for death, and thus it is meaningful even for patients who have died.

If the between-imputation variance calculated while combining some analysis results of the multiply-imputed datasets is zero then that specific analysis will not be performed using multiple imputation. Instead, the observed data will be used to perform the same analysis.

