**Table KHAA.6.4. Description and Derivation of Primary, Key Secondary, and Associated Supportive Analyses**

Measure	Description	Variable	Derivation / Comment	Definition of Missing
NIAID-OS	Using data from the COVID-19 Clinical Status Assessment, results will be calculated for ordinal scales currently being used in other studies, and in this study, to measure clinical outcomes in patients treated for COVID-19, in particular the NIAID-OS. The NIAID-OS is as follows:	Patients who die or progress to requiring ventilation	Proportion of patients who progress to ventilation or death. In order to be counted as having this event: 
 
• Patients who start at OS 4 or 5 must progress to at least OS 6.
 
• Patients who start at OS 6 must progress to at least OS 7.
 
	Missing if NIAID-OS is missing and the variable status cannot be identified using remaining data.
	1. Not hospitalized, no limitations on activities	Ventilator-free days (days free of invasive mechanical ventilation)	Total number of days patients are alive and have a NIAID-OS less than 7	Missing if patient's NIAID-OS is missing for any day.
	2. Not hospitalized, limitation on activities and/or requiring home oxygen	1-point improvement in OS (at days 4, 7, 10 and 14)	Proportion of patients with baseline NIAID-OS minus NIAID-OS $\geq 1$	Missing if either baseline NIAID-OS is missing or if the observed NIAID-OS is missing on the day of assessment of 1-point improvement
	3. Hospitalized, not requiring supplemental oxygen – no longer requires ongoing medical care: (This would include those kept in hospital for quarantine/infection control, awaiting bed in rehabilitation facility or homecare, etc.)	Time to recovery	Time to reach NIAID-OS 1, 2, or 3 for the first time. The date reached is the first full day that OS 1, 2, or 3 is the patient's maximum OS for the day.	Missing if NIAID-OS is missing and time to event of interest cannot be identified using remaining data
	4. Hospitalized, not requiring supplemental oxygen – requiring ongoing medical care (COVID-19 related or otherwise)	Overall improvement (at days 4, 7, 10, and 14)	NIAID OS	Missing if observed NIAID-OS is missing

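### The imputation chain for the primary endpoint does not condition on the patient's own baseline OS, so an OS 5 starter with no status after baseline can be imputed straight into an event

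*SAP*

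**What the plan says.** **The chain.** SAP Appendix 2, part 2, fixes its length: "Daily transitions were divided into 4 bins as follows: (bin 1) includes the first 6 transitions", bin 2 holds 7 more, then "bin 3) includes the next 7 transitions; and (bin 4) the final 7 transitions". The initial probabilities "represent the probability that a patient will be in state" j on Day 1. Part 4 draws a missing Day 1 state from gamma(1) and each later state from the one before it. Neither the likelihood, the forward and backward recursions, nor the simulation steps contain a baseline term.

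**The strata.** SAP 6.4.3 runs the imputation separately in six strata, three per arm. One of them is "baricitinib patients with baseline NIAID-OS of 5 or 6 and no baseline steroid use". Four of the six pool OS 5 with OS 6. The stated reason is to keep enough patients in each stratum.

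**The records.** Protocol 8.1.1 collects two separate records that touch Day 1: "On Day 1, the patient's status at randomization will be reported", and "On Day 2 the status will be reported for the period from randomization to midnight on Day 1". Daily entries then continue to Day 29, which covers Day 28.

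**The event.** SAP Table KHAA.6.4 sets the threshold by starting score: "Patients who start at OS 4 or 5 must progress to at least OS 6". OS 6 starters must reach at least OS 7. Table KHAA.6.5 makes logistic regression on the imputed data the primary analysis in both populations.

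**The content of Day 1.** SAP 6.1 uses the worst score of the day for primary and key secondary OS analyses. Only the duration-of-hospitalization row of Table KHAA.6.4 says that baseline is merged with the rest of Day 1.

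**The concern.** The primary event is defined relative to the patient's own baseline score, but the imputation that generates missing events knows only that the patient started at OS 5 or OS 6. Appendix 2 itself notes that patients tend to stay in one state for days, so the baseline score is the best available predictor of Day 1. The analysis model adjusts for OS 4, 5 and 6 separately (SAP 6.1.4), so the imputation is coarser than the model it feeds.

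The exposed patients are those with a baseline status and little or nothing afterwards. They stay in the ITT analysis. The supportive LOCF analysis cannot reveal the problem, because SAP 6.4.2 restricts LOCF to patients with a postbaseline value. The OS 5/6 strata without steroids correspond to Population 2, so both primary tests are exposed.

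**Working it through.** **1. Count.** 6 + 7 + 7 + 7 = 27 transitions, so 28 positions, with bins ending on Days 7, 14, 21 and 28. Records under Protocol 8.1.1: 1 at randomization + 28 entries (Days 2 to 29) = 29. The chain matches the 28 study days. The record with no stated place is the randomization status.

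**2. Which record is Day 1?** Three readings are possible:
- *The rest of Day 1.* This is best supported: Table KHAA.6.4 separates baseline from the rest of Day 1 and merges them for one endpoint only. Own baseline is then outside the chain.
- *The worst of baseline and the rest of Day 1.* This is compatible with SAP 6.1 but not stated for the primary endpoint. Nothing says what happens when the rest of Day 1 is missing.
- *The randomization status.* Baseline is then in the chain, but position 28 is Day 27, which fits poorly with a by-Day-28 endpoint.

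**3. The draw with nothing observed after baseline** (first reading). All backward variables equal 1, so gamma(1) reduces to pi for the pooled stratum.

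The documents give no transition rates. The following daily rates are assumed, with 'recovered' standing for the recovered or discharged states:
- From OS 5: recovered 3%, OS 4 12%, OS 6 h, OS 7 0.3%, death 0.2%, else stay; h = 2% or 3.5%.
- From OS 6: OS 4 1%, OS 5 10%, OS 7 3%, death 1%, stay 85%.
- From OS 4: recovered 25%, OS 5 5%, OS 6 1.5%, OS 7 0.4%, death 0.1%, stay 68%.
- From OS 7: OS 5 2%, OS 6 3%, death 5%, stay 90%.
- From recovered: OS 5 0.3%, OS 6 0.1%, death 0.1%, stay 99.5%.

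Let s be the OS 6 share of the stratum (assumed 20-40%). The chance of being at OS 6 or above on Day 1 is:
- pooled: (1 - s)(h + 0.005) + s(0.89)
- from own OS 5 baseline: h + 0.005

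For s = 0.2, h = 0.02: 0.8 × 0.025 + 0.2 × 0.89 = 0.198, against 0.025. For s = 0.4, h = 0.035: 0.6 × 0.040 + 0.4 × 0.89 = 0.380, against 0.040.

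**4. Event by Day 28.** Running 27 further transitions from each starting distribution gives the following (pooled draw / own baseline):

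| h | s | Day 1 at OS 6 or above, OS 5 starter | 28-day event, OS 5 starter | 28-day event, OS 6 starter | Net excess per patient, OS 5 and 6 mixed |
|---|---|---|---|---|---|
| 2% | 20% | 19.8% / 2.5% | 37% / 24% | 16% / 33% | +0.073 |
| 2% | 30% | 28.4% / 2.5% | 44% / 24% | 18% / 33% | +0.096 |
| 2% | 40% | 37.1% / 2.5% | 51% / 24% | 20% / 33% | +0.110 |
| 3.5% | 20% | 21.0% / 4.0% | 43% / 31% | 17% / 34% | +0.064 |
| 3.5% | 30% | 29.5% / 4.0% | 49% / 31% | 20% / 34% | +0.085 |
| 3.5% | 40% | 38.0% / 4.0% | 55% / 31% | 22% / 34% | +0.097 |

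The last column is (1 - s) × (OS 5 difference) + s × (OS 6 difference), from unrounded values.

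**5. Day 1 missing but Day 2 observed at OS 5.** gamma(1) now weights each Day 1 state by its chance of moving to OS 5. The chance of OS 6 or above on Day 1 falls to 3.2-7.8%, against 0.3-0.5% from own baseline.

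**6. Effect on the trial.** The shift in the overall event rate is k × (OS 5 difference) / 1400. For k = 14 OS 5 starters it is 0.12-0.27 points; for k = 70 it is 0.61-1.35 points. For 14 patients in the stratum's OS 5/6 mix it is 14 × 0.064 to 0.110 / 1400 = 0.06-0.11 points.

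**The case against.** The strongest reply is that this is a gap in wording. The SAP never says baseline is ignored. The worst-score-of-the-day rule could bring it into Day 1, and if a missing remainder of the day then defaulted to baseline, nothing would be drawn. SAP 6.4 lets outcomes be derived from other clinical data before imputation, and Appendix 2 lets the indicator q be altered for known states. The pooling was deliberate and explained. Patients expected to be discharged within 72 hours are excluded, and hospitalization status is completed daily regardless of contact, so few patients should have nothing after baseline.

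Most of this stands as a limit on size and certainty. It does not remove the point: none of these provisions says that baseline OS is used, and the only restriction specified for q is that a patient is known not to be dead.

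A reader might infer four stronger things that the documents do not support:
- *That 28 positions for 29 records is a counting error, or that Day 28 is lost.* Twenty-eight positions match Days 1 to 28. Day 28 drops out only under the least plausible reading of Day 1.
- *That any missing Day 1 is a pure draw from the pool.* gamma(1) conditions on every later observed state, so a pure draw needs nothing observed after baseline.
- *That events are only added.* OS 6 starters lose imputed events, which offsets part of the OS 5 excess.
- *That one arm gains.* Imputation runs separately by arm under the same rule, so there is no built-in direction.

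**Conclusion.** The point holds in limited form. As the algorithm is written, and on the best-supported reading of Day 1, an OS 5 starter with no status after baseline has about a 20-38% chance of being imputed into an immediate primary event, against 2.5-4% from the patient's own baseline. The imputed 28-day risk is 37-55% instead of 24-31%. For an OS 6 starter it is 16-22% instead of 33-34%. These figures rest on the assumed daily rates and an assumed OS 6 share of 20-40%. The structural result needs neither: the excess is roughly the stratum's OS 6 share.

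OS 4 starters fall in the remaining strata and are untouched by the pooling. The documents do not give the number of affected patients, and it is probably small. The likely effect is therefore a little misclassification in both arms, not a threat to the trial's conclusion. It is still worth correcting, because the specified algorithm can create the primary event without using the score that defines it.

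**What to change.** State in Appendix 2 which status record fills the Day 1 position. Then add the randomization status as an observed position 0, giving 29 positions and 28 transitions. SAP 6.1 already drops patients without the model covariates, and baseline severity is one of them, so position 0 is known for every patient in the primary model. Day 1 is then imputed from the patient's own OS 5 or OS 6, Day 28 stays in the chain, and pi no longer drives any draw. The six strata can stay as they are, which preserves the stratum sizes that the SAP wanted to protect.

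The cost is one more column in the imputation input and a short wording change, to be settled before the study team is unblinded. There is one small downside. The step from baseline to the rest of Day 1 covers only part of a day, so sharing a bin with full-day steps would strain the assumption of equal transition probabilities within a bin. It may need its own bin, for example 1 + 6 + 7 + 7 + 7 = 28.

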### 3) Additional Notation Conventions:

To simplify the notation, we will drop the index for individuals. We used the notation  $\mathbf{h}_{t_1:t_2}$  to represent a vector of states from day  $t_1$  to  $t_2$  inclusive. We define  $\mathbf{h}^{obs}$  as the observed states where the missing values will be coded as belonging to state 9 and patients who are missing but not dead will be defined as being in state 10. We also define the flowing indicator function:

$$q(\mathbf{h}^{obs}, h) = \begin{cases} I[h = \mathbf{h}^{obs}] & h^{obs} \leq 8 \\ 1 & h^{obs} = 9 \\ I[h \neq 8] & h^{obs} = 10 \end{cases}$$

The  $q(h^{obs}, h)$  can be flexibly altered to account knowledge about which states a patient with missing data may be. The transition probability in our case has the form:

$$P_{b_j} = \begin{bmatrix} p_{b_j11} & p_{b_j12} & \dots & p_{b_j17} & p_{b_j18} \\ p_{b_j21} & p_{b_j22} & \dots & p_{b_j27} & p_{b_j28} \\ \vdots & \vdots & \ddots & \vdots & \vdots \\ 0 & 0 & \dots & 0 & 1 \end{bmatrix},$$

and initial probability has the form:

$$\pi = (\pi_1, \pi_2, \dots, \pi_7, \pi_8).$$

Using the function above, the likelihood may be rewritten as:

$$\begin{aligned} L(\theta | \mathbf{h}_{1:T}^{obs}) &= \sum_{\mathbf{h}_{1:T}} P(H_1 = h_1, \dots, H_T = h_T) \prod_{j=1}^T q(h_j^{obs}, h_j) \\ &= \sum_{\mathbf{h}_{1:T}} \pi_{h_1} q(h_1^{obs}, h_1) \prod_{j=1}^{T-1} P_{b_j}(h_{j+1} | h_j) q(h_{j+1}^{obs}, h_{j+1}) \end{aligned}$$

